4.2. Exclusion Criteria

- Prior treatment with LV.
- Prior immuno-oncology therapy (e.g., therapies affecting the PD-L1, PD-L2, CTLA-4, or CD137 pathways, or any other antibody or drug specifically targeting T cell costimulation or checkpoint pathways).
- Pre-existing neuropathy of Grade ≥2.
- 15. History of another malignancy within 3 years prior to screening, with the exception of those with a negligible risk of metastasis or death (e.g., approximate 5-year OS of ≥90%), such as adequately treated carcinoma in situ of the cervix, non-melanoma skin carcinoma, localized prostate cancer, ductal carcinoma in situ, or Stage I uterine cancer.
- 16. History of carcinomatous meningitis or active central nervous system (CNS) metastases. Patients are eligible if CNS metastases are adequately treated and patients have neurologically returned to baseline (except for residual signs or symptoms related to the CNS treatment) for at least 4 weeks prior to enrollment. In addition, patients must be completely off corticosteroids.
- History of leptomeningeal carcinomatosis.
- Active infection requiring systemic treatment ≤7 days before dose of study drug. Routine antimicrobial prophylaxis is permitted.
- 19. Known to be positive for hepatitis B by surface antigen expression, active hepatitis C infection (positive by polymerase chain reaction [PCR] or on antiviral therapy for hepatitis C within the last 6 months), or a known history of being seropositive for HIV. Patients who have been treated for hepatitis C infection are permitted if they have documented sustained virologic response of 12 weeks.
- 20. Documented history of a cerebral vascular event (stroke or transient ischemic attack), unstable angina, myocardial infarction, or cardiac symptoms consistent with congestive heart failure, Class III-IV, by New York Heart Association criteria within 6 months prior to study enrollment (See Appendix I).
- Ongoing, clinically significant toxicity (Grade 2 or higher) associated with prior treatment including systemic therapy, radiotherapy, or surgery.
- 22. Has received prior radiotherapy within 2 weeks of start of study treatment. A patient is also excluded if radiotherapy occurred more than 2 weeks prior to start of study treatment but the patient has not recovered from radiation-related toxicities, requires corticosteroids, or has had radiation pneumonitis.

- 23. Active autoimmune disease that has required systemic treatment in past 2 years (i.e., with use of disease modifying agents, corticosteroids, or immunosuppressive drugs). Replacement therapy (e.g., thyroxine, insulin, or physiologic corticosteroid replacement therapy for adrenal or pituitary insufficiency, etc.) is not considered a form of systemic treatment.
- History of interstitial lung disease.
- Current pneumonitis, or history of (non-infectious, including radiation induced) pneumonitis that required steroids.
- 26. Has a diagnosis of immunodeficiency or is receiving chronic systemic steroid therapy (in doses exceeding 10 mg daily of prednisone equivalent) or any other form of immunosuppressive therapy within 7 days prior to the first dose of study treatment. The use of corticosteroids for physiological replacement may be approved after consultation with the sponsor.
- 27. Patients who are breastfeeding, pregnant, or planning to become pregnant from time of informed consent until 6 months after final dose of study drug administration.
- Known hypersensitivity to any excipient contained in the drug formulation of LV or pembrolizumab.
- 29. Has received transfusion of blood products (including platelets or red blood cells) or administration of colony stimulating factors (including G-CSF, granulocyte macrophage colony-stimulating factor [GM-CSF], or recombinant erythropoietin) within 4 weeks prior to study Day 1.
- 30. Other serious underlying medical condition that, in the opinion of the investigator, would impair the ability to receive or tolerate the planned treatment and follow-up; any psychiatric or substance abuse disorders that would interfere with the participant's ability to cooperate with the requirements of the trial.
- Has received a live vaccine within 30 days of planned start of study therapy.
 - a. Note: seasonal influenza vaccines for injection are generally inactivated flu vaccines and are allowed; however intranasal influenza vaccines (e.g., Flu-Mist) are live attenuated vaccines and are not allowed.
- 32. Has not recovered (e.g., to ≤ Grade 1 or to baseline) from AEs due to a previously administered therapy.
- Has had an allogenic tissue/solid organ transplant.

4.3. Childbearing Potential

A patient of childbearing potential is defined as anyone born female who has experienced menarche and has not undergone surgical sterilization (e.g., hysterectomy, bilateral salpingectomy, bilateral oophorectomy) or completed menopause. Menopause is defined

clinically as 12 months of amenorrhea in a woman over age 45 in the absence of other biological, physiological, or pharmacological causes.

4.4. Removal of Patients from Therapy or Assessment

Seagen or their designee must be notified if a patient is withdrawn from study treatment or from the study. The reason(s) for withdrawal must be documented in the patient's medical records and/or case report form (CRF).

4.4.1. Discontinuation of Study Treatment

A patient's study treatment may be discontinued for any of the following reasons:

- Progressive disease (PD)
- AE
- Pregnancy
- Investigator decision
- Patient decision, non-AE
- Study termination by sponsor
- Other, non-AE

Patients who discontinue from study treatment will remain on study for follow-up unless they withdraw consent.

Discontinuation of pembrolizumab may be considered for patients who have attained a confirmed CR that has been treated for at least 8 cycles (24 weeks) and had at least 2 treatments with pembrolizumab beyond the date when the initial CR was declared.

Patients who discontinue pembrolizumab may continue to receive LV with medical monitor approval (see Section 5.2.5). Similarly, patients that discontinue LV may continue to receive pembrolizumab with medical monitor approval (see Section 5.3.5).

4.4.2. Patient Withdrawal from Study

Any patient may be discontinued from the study for any of the following reasons:

- Patient withdrawal of consent
- Study termination by sponsor
- Completion of protocol specified safety follow-up (see Section •)
- Lost to follow-up
- Death
- Other

TREATMENTS

5.1. Treatments Administered

All patients will receive LV, the investigational agent under study in this protocol, in combination with pembrolizumab. LV will be administered first, followed by pembrolizumab approximately 60–90 minutes after infusion of LV is complete.

5.2. Investigational Study Drug: LV

LV is an ADC consisting of the anti-LIV1A mAb hLIV22 conjugated to MMAE, a synthetic analog of the naturally occurring tubulin-binding agent, dolastatin 10.

Detailed information describing the preparation, administration, and storage of LV is located in the LV Pharmacy Instructions.

5.2.1. Description

LV is a sterile, preservative-free, white to off-white lyophilized cake or powder for reconstitution for IV administration. LV is supplied by Seagen in single-use glass vials. Each drug product vial contains LV for Injection, trehalose, histidine, and polysorbate 80. Drug product vials are labeled with a nominal content of 40 mg/vial. Each vial contains 45 mg of LV. Enough overfill is included to allow for 40 mg of LV to be withdrawn for use.

When reconstituted with 8.8 mL Water for Injection (WFI), United States Pharmacopeia (USP), the concentration of reconstituted LV product is 5 mg/mL. The reconstituted drug product is a clear to slightly opalescent, colorless to light yellow solution with no visible particulate matter. The pH is approximately 6.0. The reconstituted solution is subsequently diluted in sterile 0.9% Sodium Chloride for Injection, USP, for IV administration.

5.2.2. Method of Procurement

LV will be provided by the sponsor.

5.2.3. Dose and Administration

5.2.3.1. All Parts

In the absence of IRRs, the infusion rate for all patients should be calculated in order to achieve a 30-minute infusion period. However, given the variability of infusion pumps from site to site, a window between -5 minutes and +10 minutes is permitted (i.e., infusion time is 30 minutes -5 min/+10 min).

LV must not be administered as an IV push or bolus. LV should not be mixed with other medications.

Weight-based dosing of LV is based on the patient's actual body weight. Doses must be adjusted for patients who experience a ≥10% change in weight from baseline. Patient weight must be measured during all relevant assessment windows as described in the schedule of events (Appendix A). If weight is assessed per institutional standard of care at a timepoint not required per protocol (e.g., Day 8 or Day 15) and there is a ≥10% change in weight from baseline, LV

dose must be adjusted accordingly. Other dose adjustments for changes in body weight are permitted per institutional standard.

5.2.3.2. Parts A and B

Prior to Amendment 2, LV at a dose of 2.5 mg/kg (capped at 80 kg per infusion) will be administered on Day 1 of every 21-day cycle by IV infusion given over approximately 30 minutes. For patients treated under Amendment 2 and later, the maximum weight cap per infusion will be increased from 80 kg to 100 kg. Any patient receiving >200 mg LV per infusion (weight >80 kg) is required to receive prophylactic G-CSF. For patients weighing ≥100 kg, dosing will be based on 100 kg. In consultation with the sponsor, eligible patients already on treatment prior to Amendment 2, may have their maximum weight cap per infusion increased to 100 kg or remain at 80 kg if they are receiving benefit (CR, PR, or SD).

Prior to Amendment 2, for patients weighing greater than 80 kg, dose calculations will be based on 80 kg (including dose reductions). For patients treated under Amendment 2 and later, the maximum weight cap per infusion will be increased from 80 kg to 100 kg, therefore, the maximum dose will be 250 mg per infusion when dosing at 2.5 mg/kg and 200 mg per infusion when dosing at 2.0 mg/kg. For patients who receive >200 mg LV per infusion, prophylactic G-CSF administration is required and will be given to patients on the day after study treatment is given, with a visit window of Day 2–4. Rounding is permissible within one milligram of nominal dose.

5.2.3.3. Part C

LV will be given on Day 1, Day 8, and Day 15 in every 3-week cycle.

At least 7 days must elapse between administrations of LV. There will be no weight cap per infusion. The maximum dose will be 200 mg per infusion.

5.2.3.4. Part D

LV will be given at a dose of 1.5 mg/kg by IV infusion over approximately 30 minutes on Day 1 and Day 8 in every 21-day cycle. LV will **NOT** be administered on Day 15 for patients enrolled in Part D.

At least 7 days must elapse between administrations of LV. The maximum dose will be 200 mg per infusion.

5.2.3.5. LV Dosing Criteria

Dose modification guidelines for LV are detailed in Table 3 and Table 6. The following laboratory criteria must be met on Day 1 of each cycle prior to LV administration:

- Neutrophil count ≥1000/µL (≤ Grade 2)
- AST ≤ Grade 2
- ALT ≤ Grade 2
- Total bilirubin ≤ Grade 2
- Blood glucose ≤250 mg/dL or ≤13.9 mmol/L

If these criteria are not met on the day of dosing, hold the LV dose until criteria are met. In addition, hold LV dosing for patients with \geq Grade 2 peripheral neuropathy. Additional information on LV dose modifications can be found in Table 3 and Table 6. Please see Table 7 for information on pembrolizumab dosing.

In Part C, neutrophil count must also be $\geq 1000/\mu L$ (\leq Grade 2) prior to LV administration on Days 8 and 15 of each cycle.

In Part D, neutrophil count must also be $\geq 1000/\mu L$ (\leq Grade 2) prior to LV administration on Day 8 of each cycle.

5.2.4. Overdose

In the event of an overdose >10% of LV, the site should notify the sponsor as soon as they are aware of the overdose. The patient should be closely monitored for adverse reactions, particularly neutropenia. Supportive care per institutional standards should be administered. Adherence to current clinical practice guidelines for the use of white blood cell (WBC) growth factors (see Appendix L) is strongly recommended for the management of neutropenia and febrile neutropenia (Crawford 2010; Smith 2015).

5.2.5. Dose Modifications

Patients who experience DLT in Cycle 1 (the DLT evaluation period) should not receive further treatment with LV and pembrolizumab unless clinical benefit is observed, and the AE(s) is adequately managed with severity improving to Grade 1 or lower. Subsequent doses will be defined by the medical monitor in discussion with the site investigator in the context of the type of AE(s) observed.

In the event a patient is unable to tolerate their dose level, additional treatment cycles (Cycle 2 or later) may be administered at a lower dose level. Consultation with the medical monitor is strongly encouraged.

Patients who discontinue pembrolizumab due to a pembrolizumab-related AE may continue LV. Similarly, patients who discontinue LV for a LV-related AE may continue pembrolizumab.

5.2.5.1. Parts A and B

If a patient has a clinically significant, unresolved AE on Day 1 of any cycle, the start of the cycle may be delayed for up to 14 days. Delays of >14 days must be approved by the medical monitor.

Dose modifications for LV treatment associated toxicity are described in Table 3. Any deviations from these modifications should be discussed with the medical monitor.

Prior to Amendment 2, the maximum doses after modification are:

- 160 mg for patients reduced to 2.0 mg/kg
- 120 mg for patients reduced to 1.5 mg/kg

For patients treated under Amendment 2 and later, the maximum doses after modification are:

- · 200 mg for patients reduced to 2.0 mg/kg
- 150 mg for patients reduced to 1.5 mg/kg
- 125 mg for patients reduced to 1.25 mg/kg

Amendment 11; 19-Oct-2023

Page 46 of 152

Table 3: Required dose modifications for LV-associated toxicities (Parts A and B)

Toxicity	Grade 1	Grade 2	Grade 3	Grade 4
Peripheral neuropathy ^a	Continue at same dose level	Withhold until toxicity resolves to ≤ Grade 1; then resume treatment at the next lower dose level	Withhold until toxicity resolves to ≤ Grade 1, then resume treatment at the next lower dose level	Discontinue treatment
Hyperglycemia				ame day of dosing. Dose may be delivered on the ol/L and patient is clinically and metabolically
Non-hematologic ^a (except peripheral neuropathy and elevated blood glucose)	Continue at same dose level	Continue at same dose level	Withhold dose until toxicity is ≤ Grade 2 or has returned to baseline, then resume treatment at same dose level ^b	Withhold dose until toxicity is ≤ Grade 2 or has returned to baseline, then reduce dose to the next lower dose level and resume treatment, or discontinue at the discretion of the investigator ^{b,c}
Hematologic ^a	Continue at same dose level	Continue at same dose level	Withhold until toxicity resolves to ≤ Grade 2 or baseline. de For neutropenia, strongly consider WBC Growth Factor support, then resume treatment at the same dose level. Prophylactic WBC Growth Factor support should be strongly considered for subsequent cycles. (See Appendix L)	Withhold until toxicity resolves to ≤ Grade 2 or baseline. de For neutropenia, strongly consider WBC Growth Factor support, then resume treatment at the same dose level. Prophylactic WBC Growth Factor support is required for all subsequent cycles. If Grade 4 neutropenia recurs despite WBC Growth Factor support, consider dose reduction to 2.0 mg/kg or discontinuation (See Appendix L)
Febrile neutropenia ^a			until febrile neutropenia resolves at baseline then resume treatment at t Factor support is required for all subs	red for treatment of febrile neutropenia. Withhold nd neutrophil count returns to ≤ Grade 2 or the same dose level. Prophylactic WBC Growth equent cycles. If febrile neutropenia recurs rt, consider dose reduction to 2.0 mg/kg or

Note: Prior to Amendment 2, for patients weighing >80 kg, dosing will be based on 80 kg. For patients treated under Amendment 2 and later, the maximum weight cap per infusion will be increased from 80 kg to 100 kg. Patients who receive >200 mg LV per infusion are also required to be administered prophylactic G-CSF.

a Only 2 dose reductions are allowed. Additional toxicities should be managed with dose delays.

b Patients who develop Grade 3 or 4 electrolyte laboratory abnormalities may continue study treatment without interruption if a management plan consistent with institutional practice and regular monitoring are put in place.

c Treatment should be discontinued for patients who experience Grade 4 IRRs.

d Support with blood product transfusions allowed per institutional standard of care.

e Patients who develop Grade 3 or 4 lymphopenia may continue study treatment without interruption.

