3.1.2. Part B: Expansion

Part B is designed to further evaluate the safety and antitumor activity of the combination of LV and pembrolizumab and to maximize the benefit-risk profile. This part of the study will be conducted in 2 cohorts. Patients will enroll sequentially into Cohort 1 followed by Cohort 2. Part B Cohort 1 will receive the MAD of LV 2.5 mg/kg, (capped at 100 kg) in combination with pembrolizumab. Part B Cohort 2 will receive a dose of LV 2.0 mg/kg (capped at 100 kg), in combination with pembrolizumab (see Section 3.2.3.1 for rationale of Part B Cohort 2). Patients receiving >200 mg LV per infusion are required to be administered prophylactic granulocyte-colony stimulating factor (G-CSF).

Patients will receive LV and pembrolizumab q3wk. Pembrolizumab, 200 mg IV will be given per the US prescribing information on the same day as LV, approximately 60-90 minutes following LV infusion.

Approximately 73 patients will be enrolled in Part B of the study (approximately 48 in Cohort 1 and approximately 25 in Cohort 2).

The SMC and ISMC will continue to monitor the safety of LV and pembrolizumab. The SMC will meet regularly during Part A but convene as needed in Part B. The ISMC will meet periodically.

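### Table 3's recurrent-neutropenia rows name 2.0 mg/kg whatever the current dose, which is no reduction for patients already at 2.0 mg/kg and does not fit the lower levels in Section 5.2.5.1

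*Protocol*

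**What the plan says.** **The rule.** Table 3 in Protocol Section 5.2.5.1 is headed as required modifications and covers Parts A and B together. It is not split by cohort, starting dose or current dose. When Grade 4 neutropenia comes back in spite of growth factor support, the Grade 4 hematologic cell asks sites to "consider dose reduction to 2.0 mg/kg or discontinuation". The febrile neutropenia cell carries the same target; its last legible words are "consider dose reduction to 2.0 mg/kg or". The end of that cell, and part of its condition, are broken in the extracted text.

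**Starting doses.** Protocol Section 3.1.2 puts Cohort 1 at 2.5 mg/kg and states: "Part B Cohort 2 will receive a dose of LV 2.0 mg/kg". Section 3.2.3.1 says that both doses were also tested in Part A. Section 9.1.2 expects about 25 patients in Cohort 2 and about 30 at 2.0 mg/kg once Part A is added.

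**Levels the section recognises.** Section 5.2.5.1 gives maximum doses after modification at 2.0 and 1.5 mg/kg and, for patients treated under Amendment 2 and later, also "125 mg for patients reduced to 1.25 mg/kg".

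**Other rows and footnote.** The Grade 2 and 3 peripheral neuropathy cells and the Grade 4 non-hematologic cell step down one level from the current dose and name no figure. Footnote a, attached to both neutropenia rows among others, caps reductions at two and sends further toxicity to dose delay.

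**General provisions.** Section 5.2.5 permits a lower dose level from Cycle 2 for a patient who cannot tolerate the current one and strongly encourages consulting the medical monitor. Section 5.2.5.1 says that departures from Table 3 should be discussed with the medical monitor.

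**The concern.** A fixed target works only for patients above it. The two rows suit a patient at 2.5 mg/kg. They have no meaning for a cohort that starts at 2.0 mg/kg, or for a Cohort 1 patient already reduced for another toxicity. The trigger is a repeated serious hematologic event after supportive treatment, which is when a site most needs a clear instruction.

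There is also a reporting side. Section 3.2.3.1 says Cohort 2 was added to assess tolerability better at the lower dose. The SAP (Section 6.7.1) tabulates treatment-emergent events leading to LV dose reduction and to treatment discontinuation, and by Section 5.1 these are shown by dose level. If sites followed the rows literally, a patient at 2.5 mg/kg would have a real reduction open to them and a patient at 2.0 mg/kg would not.

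**Working it through.** **1. Reproduce the section's own levels.** Maximum dose = level (mg/kg) × weight cap (kg).

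- Before Amendment 2 (cap 80 kg): 2.0 × 80 = 160 mg; 1.5 × 80 = 120 mg.
- Amendment 2 and later (cap 100 kg): 2.0 × 100 = 200 mg; 1.5 × 100 = 150 mg; 1.25 × 100 = 125 mg.

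All five match Section 5.2.5.1. The section therefore does recognise levels below 2.0 mg/kg in Parts A and B. Section 3.2.3.1 dates the addition of Cohort 2 to Amendment 4, so its patients fall under the second list.

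**2. Apply the named target to each dose.** Change = 2.0 − current dose.

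| Current dose (mg/kg) | Change to 2.0 (mg/kg) | Relative change |
|---|---|---|
| 2.5 | −0.5 | −0.5/2.5 = −20% |
| 2.0 | 0 | 0% |
| 1.5 | +0.5 | +0.5/1.5 = +33% |

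The row gives a reduction at one of these three doses.

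**3. Compare with footnote a.** The footnote allows up to two reductions. A fixed 2.0 mg/kg target can supply one from 2.5 mg/kg and none from 2.0 mg/kg. The footnote is a ceiling and promises no one two reductions. But a ceiling of two makes little sense on a row that can supply none for a planned cohort.

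**4. Compare with the parallel table.** For the same recurrent events in Parts C and D, Table 6 steps down from the current dose and points to Tables 4 and 5 for the level. The difficulty is confined to Table 3.

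**5. Who could be reached.** Cohort 2 is 25 of 73 planned Part B patients (25/73 = 34%). Adding Part A gives about 30, so about 30 − 25 = 5 come from Part A. Patients started at 2.5 mg/kg and already reduced come on top; the documents give no count.

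**6. Who would trigger the row.** The Grade 4 row needs a recurrence despite growth factor support. No figure is given for that. The nearest is in Section 3.2.3.2: Grade 3 or 4 neutropenia in 13% of 88 Part A and B patients, both doses pooled, at 2 December 2019. Assuming that rate at 2.0 mg/kg, 0.13 × 30 = 3.9, or about 4 patients with any Grade 3 or 4 neutropenia. Recurrent Grade 4 events are a subset of these, so on this assumption the range is 0 to about 4 among patients starting at 2.0 mg/kg.

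**The case against.** The case on the other side has five parts.

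- **The wording is advisory.** The cell asks sites to consider a reduction and also offers discontinuation. Nothing in the protocol forbids going below 2.0 mg/kg.
- **There is a route to a lower dose.** Sections 5.2.5 and 5.2.5.1 provide one through the intolerance provision and the medical monitor. A reader might infer that a patient at 2.0 mg/kg can only stay on the same dose or stop. The documents do not support that.
- **Few patients are involved.** A reader might take about 30 as the number affected. That is the number starting at 2.0 mg/kg, not the number with a recurrent event. Section 3.2.3 also reports no febrile neutropenia among 19 monotherapy patients at 2.0 mg/kg.
- **No formal comparison depends on it.** SAP Section 5.7 plans no hypothesis testing, and the reduction and discontinuation tables are descriptive. A reader might infer that the comparison of the two doses is distorted. The documents allow neither the size nor the presence of such an effect to be established.
- **It may be late.** Planned enrollment in Parts A and B is 12 + 73 = 85 to 24 + 73 = 97, and 88 had been treated by December 2019. The documents do not show whether anyone remains on treatment at 2.0 mg/kg.

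All five limit the consequence, and they stand. None of them makes the two rows correct. The workaround relies on general text and case-by-case discussion to depart from a table headed as required, and the rows still disagree with the levels listed just above them.

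**Conclusion.** The point holds as an internal contradiction in an operational safety rule. The recurrent Grade 4 neutropenia and febrile neutropenia rows of Table 3 give a reduction only to patients above 2.0 mg/kg. For about 25 patients in Cohort 2, about 30 with Part A, and anyone already reduced to 2.0 mg/kg or below, the named reduction is nil or points upward. It does not fit the 1.5 and 1.25 mg/kg levels in Section 5.2.5.1, the relative wording of other rows, or footnote a.

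The practical effect is smaller than those counts suggest. It falls on the subset with recurrent events, whose number the documents do not give, and sites have a way round it. Sample size, error rates and the primary endpoint are untouched.

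For the Grade 4 row this rests on complete text. For the febrile neutropenia row the 2.0 mg/kg target is legible but the cell is cut off, so its remaining alternatives should be read in the source document.

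**What to change.** Reconcile the Grade 4 neutropenia and febrile neutropenia rows of Table 3 with the levels in Section 5.2.5.1, with footnote a and with the Cohort 2 starting dose, so that the instruction has a meaning at every current dose. The clinical team must decide the content; no dose is proposed here. The cost is the wording of two table cells.

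If no Part A or B patient is still on treatment, the useful step is a sentence in the clinical study report saying how recurrent neutropenia was handled in patients at 2.0 mg/kg or below, so that the reduction and discontinuation tables can be read correctly.
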